#### DOR

For subjects with complete response or partial response, the duration of response is defined as the time from the date of first response to the date of disease progression or death whichever is earlier, and subjects with no disease progression or death will be censored on the date of the last imaging assessment.

Kaplan-Meier method will be used for the analysis of DOR to evaluate the median DOR and its 95% CI and the survival curves will be provided accordingly.

#### TTR

For subjects with complete response or partial response, the time to response is defined as time from the date of first dose to the date of the first objective response.

Kaplan-Meier method will be used for the analysis of TTR to evaluate the median TTR and its 95% CI and the survival curves will be provided accordingly.

### **5.5.3 Subgroup Analysis**

Subgroup analysis will be conducted for subgroups including PD-L1 expression, EBV, LDH, B symptom.

### **5.5.4 Exploratory Analysis**

Correlation between gene related cancer immunity and efficacy will be explored.

## **5.6 SAFETY ANALYSIS**

Safety analysis will be conducted in safety set.

### **5.6.1 Adverse Events**

All adverse events will be coded using MedDRA dictionary for lower level term (LLT), preferred term (PT), high level term (HLT), high level group term (HLGT) and system organ class (SOC). AE

reporting period will be further defined based on onset date/becoming serious/becoming more severe as:

- Pre-treatment AE: AE occurs/becomes serious/becomes more severe before first dose of treatment and after inform consent.
- Treatment-emergent AE: AE occurs/becomes serious/becomes more severe on or after date of first dose of treatment up to last dose of study treatment+90 days
- Post treatment AE: AE occurs/becomes serious/becomes more severe on or after date of last dose of study treatment+91 days

If onset date of AE is missing or partial missing, determination of AE reporting period will be based on rules in Section 4.3.

- **Overview of adverse event**

Listing will be provided for pre-treatment and post-treatment AE.

Number and percentage of subjects who experience AE and event frequency will be summarized for:

- Treatment emergent period
  - TEAE
  - Treatment related AE (TRAE)
  - Serious AE (TESAE)
  - AE leading to death
  - TRSAE
  - TRAE leading to death
  - TEAE leading to treatment discontinuation
  - TRAE leading to treatment discontinuation
  - Important AE (Chinese regulator specific requirement only)
  - Immune-related AE (irAE)

Unless otherwise stated, SOC/PT summary will be sorted according to descending order of frequency.

- **TEAE analysis**

Number and percentage of subjects with AE will be summarized by:

- SOC and PT and by highest CTCAE grade for TEAE

- SOC and PT and by highest CTCAE grade for TRAE
- SOC and PT and by highest CTCAE grade for TEAE leading to treatment discontinuation
- SOC and PT and by highest CTCAE grade for TRAE leading to treatment discontinuation
- SOC and PT and by highest CTCAE grade for important AE (Chinese regulator specific requirement only)
- PT for TESAE
- PT for infusion-related reactions(IRR)
- **Immune-related treatment emergent AE and AE of special interest**

Immune-related treatment emergent AE:

IBI308 mechanism of action includes T-cell activation and proliferation. It may cause overactivation of immune system, which leads to systemic immune disorders. In Other immune checkpoint inhibitors (ipilimumab, nivolumab, pembrolizumab and atezolizumab) clinical data, AEs such as immune-mediated pneumonitis, diarrhea/colitis adrenal insufficiency, rash, hepatitis, endocrines disorders and peripheral neuropathy have been observed. In this study, once a subject has above AE occurring, investigators should monitor subjects's status and take proper diagnosis actions. If no alternative causes (such as disease progression, concomitant medication, other infection) and corticosteroid/other immune suppressant treatments are needed to treat the condition (except for related endocrine disorders such hypo/hyperthyroidism, hypophysitis, type 1 diabetes, adrenal insufficiency, which may not be given this treatment), the corresponding AE should be considered as potentially immune related.

AE of special interest:

AE of special interest (AESI) is defined as AE requiring special attention to understand the safety profile of the investigational product. A non-serious AE can also be considered as AESI.

AESI of this study include:

- IRR of grade 3 and above
- Diarrhea, colitis, uveitis, intestinal pneumonitis of grade 2 and above
- Suspected irAE of grade 3 and above

Number and percentage of subjects experiencing treatment emergent irAE and AESI will be summarized.

In above summaries, a subject will only be counted once according to the highest CTCAE grade and/or seriousness for each SOC or PT.

An AE with causality reported as related, possibly related or missing/undetermined will be counted as treatment related. Handling of missing seriousness and CTCAE grade can be found in Section 4.3.

- **Death**

Death during the study will be listed.

Listing of AE will include all AE, SAE, TRAE, TEAE leading to treatment discontinuation, irAE and AESI. Treatment emergent flag will be provided.

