1.2.2 Clinical study results

A phase Ia dose-escalation trial was initiated in Sep. 2016. Around 12–24 patients with advanced solid tumors who had failed standard treatment were enrolled. This dose escalation study used the standard "3 + 3" design to evaluate 4 dose levels (1 mg/kg, 3 mg/kg, 200 mg, and 10 mg/kg) of IBI308. After the completion of 1 mg/kg dose administration, subjects were randomized in a 1:1 ratio to either 3 mg/kg or 200 mg arm for independent evaluations. Dose-limiting toxicity (DLT) was observed for 28 days after the first dose for each dose arm. After completion of DLT observation, subjects were treated with IBI308 once Q2W (1 mg/kg, 3 mg/kg, or 10 mg/kg) or Q3W (200 mg) up to 24 months until progressive disease (PD), intolerable toxicity, withdrawal of ICF, or other reasons requiring treatment discontinuation (whichever occurs first).

Pharmacokinetic (PK) evaluation of IBI308 1 mg/kg was conducted in subjects with multiple tumors ($n = 3$). Preliminary results after a single-dose administration showed that IBI308 1 mg/kg reached the maximum drug exposure right after the completion of the single-dose infusion. The drug distribution was rapid after reaching the peak concentration, followed by a slow elimination ($t_{1/2} \approx 17.3$ d), which is the typical two-compartment PK characteristics of a monoclonal antibody. The elimination half-life is similar to the physiological half-life of IgG4.

The pharmacodynamic (PD) results showed that: a dosed of IBI308 1 mg/kg rapidly (24 h) saturated the peripheral PD-1 ($95.8 \pm 2.3\%$) and maintained the receptor occupancy with decreasing concentrations throughout the study (28 d, C28d: 3.70 ± 0.15 $\mu\text{g/mL}$). It is estimated that the steady state can be reached after 84 days with 6 continuous doses of IBI308 1 mg/kg

administered Q2W. If there are no significant changes in drug clearance, the steady-state trough concentration will be around 13 $\mu\text{g/mL}$ and the peripheral PD-1 receptor occupancy will be maintained.

Up to Apr. 16, 2017, the phase Ia study has enrolled 12 patients (3 for each cohort) in 4 treatment cohorts (1 mg/kg, 3 mg/kg, 200 mg, and 10mg), and evaluated the DLTs for each arm. No DLTs were observed. A total of 4 serious adverse events (SAEs) \geq grade 3 were observed in the phase Ia study, among which 3 cases of immune-related pneumonitis and lung infections are possibly related to the investigational drug.

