5.4 Principles of Managing Immune Checkpoint Inhibitor Toxicities

The mechanism of action of IBI308 is to stimulate T-cell activation and proliferation. The result is an immune hyperfunction leading to autoimmune disease involving multiple systems. Autoimmune AEs such as immune-related pneumonitis, diarrhea/enterocolitis, renal insufficiency, rash, hepatitis, endocrine disorders, and peripheral or central neuritis have been observed with the clinical application of other immune checkpoint inhibitors including ipilimumab, nivolumab,

pembrolizumab, and atezolizumab. If subjects experience the AEs described above, the signs and symptoms shall be monitored, relevant examinations shall be performed, and the cause shall be identified. If an alternative cause is not found (such as PD, concomitant medications, or infections) and glucocorticoids and/or other immunosuppressants are required, then any AE described above is considered related to IBI308-induced immune hyperfunction, and should be diagnosed as an irAE (except for endocrine events such as hyperthyroidism/hypothyroidism, hypophysitis, type I diabetes, and adrenal insufficiency which may not require immunosuppressants but are still considered as immune hyperfunction related to IBI308).

See Appendix 7 for dose adjustments and toxicity management of major potential irAEs, other potential irAEs, and infusion reactions.

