7.8.2 AESIs

AESIs refer to events that require close monitoring in order to enhance the understanding of the safety of the investigational drug. AESIs can be non-serious events.

AESIs for this trial include the followings:

- Infusion reactions \geq grade 3
- Diarrhea/colitis, uveitis, interstitial pneumonia \geq grade 2
- Suspected immune-related AEs \geq grade 3

8 Statistics

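### SAP 5.6.1 changes the protocol's AESI and irAE terms without saying so: grade 2 interstitial lung events fall outside the AESI wording, and renal and central neurological irAEs may be missed if the irAE list is read as closed

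*SAP*

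**What the plan says.** **AESIs.** Protocol 7.8.2 has three lines: infusion reactions of grade 3 or above; "Diarrhea/colitis, uveitis, interstitial pneumonia" of grade 2 or above; and suspected immune-related events of grade 3 or above. SAP 5.6.1 keeps the first and third. Its second line is "Diarrhea, colitis, uveitis, intestinal pneumonitis of grade 2 and above".

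**irAEs.** Protocol 5.4 says: "Autoimmune AEs such as immune-related pneumonitis, diarrhea/enterocolitis, renal insufficiency, rash, hepatitis, endocrine disorders, and peripheral or central neuritis have been observed". The parallel sentence in SAP 5.6.1 says: "AEs such as immune-mediated pneumonitis, diarrhea/colitis adrenal insufficiency, rash, hepatitis, endocrines disorders and peripheral neuropathy have been observed". Both documents then apply the same test: no alternative cause, and a need for corticosteroids or another immunosuppressant. Both waive the treatment requirement for endocrine events. The SAP words that waiver as "except for related endocrine disorders such hypo/hyperthyroidism, hypophysitis, type 1 diabetes, adrenal insufficiency", so adrenal insufficiency appears twice in its text and renal insufficiency does not appear in the definition.

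**Use.** SAP 5.6.1 summarises the number and percentage of subjects with treatment-emergent irAEs and AESIs. Protocol 8.4.6.2 also calls for the incidence and severity of both.

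**Declared changes.** SAP 1.5.1 gives none. SAP 1.5.2 points to the version history, which mentions only the update for protocol amendment 2.0 and a new template.

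**The concern.** The SAP states in its introduction that it provides the detailed endpoint definitions, so a programmer would be expected to work from its text. Three terms in that text do not match the protocol:

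- interstitial pneumonia has become a phrase that describes no lung event and stands beside diarrhea and colitis;
- renal insufficiency has become adrenal insufficiency, which the SAP already covers as an endocrine disorder;
- central neuritis has gone.

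The protocol treats these as expected risks of the drug. Section 1.3 names pneumonitis and renal insufficiency among the main anticipated events. Table 3 and Appendix 7 (Table 1) give separate entries to pneumonitis, renal insufficiency and neurotoxicity, and Appendix 7 distinguishes general immune-related neurotoxicity from peripheral neuropathy. Safety is a secondary objective. If the SAP wording drives the classification, the irAE and AESI summaries could understate the event types that the protocol singles out.

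**Working it through.** No formula decides this point. The check is to set the definitions side by side and then follow each kind of event through the planned summaries.

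**Step 1: the terms.**

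| Item | Protocol | SAP 5.6.1 |
|---|---|---|
| AESI line 2, lung term | interstitial pneumonia, grade 2 or above (7.8.2) | intestinal pneumonitis, grade 2 or above |
| irAE list, kidney | renal insufficiency (5.4) | absent; adrenal insufficiency in its place |
| irAE list, nervous system | peripheral or central neuritis (5.4) | peripheral neuropathy only |
| irAE list, lung | immune-related pneumonitis (5.4) | immune-mediated pneumonitis (kept) |
| AESI line 3 | suspected irAE, grade 3 or above (7.8.2) | the same |

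**Step 2: tracing events, with the SAP read literally.** For the irAE column, renal and central neurological rows assume that the event meets the test of no other cause and immunosuppressive treatment.

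| Event | irAE summary | AESI summary | TEAE tables (TRAE if related) |
|---|---|---|---|
| Interstitial lung, grade 2, no other cause, steroids needed | in, as pneumonitis | **out** (in under the protocol) | in |
| Interstitial lung, grade 2, managed without steroids or other immunosuppressants | out under both documents | **out** (in under the protocol) | in |
| Lung irAE, grade 3 or above | in | in, by line 3 | in |
| Renal or central neurological irAE, below grade 3 | **in only if the list is open** | not an AESI in either document | in |
| Renal or central neurological irAE, grade 3 or above | **in only if the list is open** | **in only if the list is open**, by line 3 | in |

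The second row is the clearest loss. For grade 2 pneumonitis, Appendix 7 presents systemic glucocorticoids as something to consider, so a case without them is foreseeable. Under the protocol it is an AESI whatever the treatment. Under the SAP wording it appears in neither special summary.

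**Step 3: what one subject is worth.** Change in incidence = 1/n. The amendment summary reports 28 enrolled. If all were treated, 1/28 = 3.6 percentage points. Over the planned range of 20 to 60 subjects (protocol 8.5, SAP 1.3), 1/20 = 5.0 and 1/60 = 1.7 points. This gives the effect per omitted subject. It does not estimate how many would be omitted.

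**Step 4: where the flags come from.** Protocol 7.5.3 has the investigator record AESI status for each event. It lists no corresponding irAE item. The SAP does not say whether either summary uses a recorded flag or a list of terms.

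**The case against.** The strongest reply is that these are slips of translation or typing with little practical effect. It has several parts.

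- **The irAE list is illustrative.** Both documents introduce it with such as, and the operative test is cause plus treatment. The SAP's reference back to the events above is not a new restriction, because protocol 5.4 is built the same way. Appendix 7 also gives a general irAE rule and a table for other potential irAEs. This stands: the renal and central neurological risk is conditional on a closed reading. It does not help the AESI bullet, which names specific events with no such as.
- **Investigators record AESI status under the protocol, whose wording is correct.** If that field feeds the table, the lung event is counted. This stands as a possibility, but the SAP does not say so.
- **The words are obvious errors.** Probably so. They are nonetheless in the document that defines the analysis, and the AESI bullet is a definition, not background.

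Two stronger readings are tempting and are not supported. A reader might infer that these events disappear from safety reporting altogether. They do not: SAP 5.6.1 tabulates all TEAEs and TRAEs by system organ class, preferred term and highest grade, and lists all AEs, without reference to irAE or AESI status. Creatinine is also part of the blood chemistry panel, which SAP 5.6.2 summarises.

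A reader might also size the gap from phase Ia, where protocol 1.2.2 reports that "3 cases of immune-related pneumonitis and lung infections are possibly related to the investigational drug". Those were serious events of grade 3 or above, and lung irAEs of that grade are still AESIs under the SAP. The count also includes lung infections, and infection is an alternative cause under both irAE definitions. It says nothing about grade 2 events.

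**Conclusion.** The departures from the protocol are real and undeclared, and their reach is limited. Read literally, the AESI bullet leaves grade 2 interstitial lung events out of the AESI summary. One managed without steroids or other immunosuppressants would be in neither special summary, since it does not meet the irAE test either. Renal and central neurological irAEs may be missed in the irAE summary and, at grade 3 or above, in the AESI summary, but only on a closed reading of the irAE list. The general tables are unaffected.

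The lung conclusion assumes that the AESI table is programmed from the SAP bullet and not from the investigator's record. The documents leave that open, and they do not show that any table has been produced from the wrong terms or that any subject has been lost. The 3.6 points per subject assumes a safety set of 28.

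**What to change.** In SAP 5.6.1:

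1. Replace the second AESI bullet with the wording of protocol 7.8.2, so that it names interstitial pneumonia of grade 2 or above.
2. Replace the irAE list with that of protocol 5.4, restoring renal insufficiency and central neuritis.
3. State that the irAE and AESI summaries use the protocol definitions.
4. State whether each flag comes from the eCRF or from a list of terms fixed before database lock. The irAE flag needs this most, because protocol 7.5.3 lists no item for it.

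The cost is a short text correction and, if that route is chosen, a term list. No new data are needed. The downside is that the reported irAE and AESI rates may be slightly higher.

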### 5.6.2 Clinical Laboratory Evaluation

Clinical laboratory evaluation includes hematological exam, blood chemistry, urine test. Local lab is used in this study and results will be analyzed and reported using international standard unit. Invalid results if marked will not be included in the analysis. Non-protocol specified laboratory test or test out of study center will not be included in the summary analysis. If abnormal is observed, AE will be reported.

Laboratory results will be summarized as normal, abnormal low, abnormal high according to normal range of each center. Abnormal values will also be reported by investigators as clinically significant or not. If “<”, “<=”, “>” or “>=” limit of quantitation, limit of quantitation will be used for summary statistics. Original results will be displayed in listing.

In SS, by visit descriptive summary will be provided for quantitative clinical laboratory evaluation. For qualitative evaluations, shift summary of change from baseline will be provided based on normal/abnormal status and clinically significant/not clinically significant status.

Listing will be provided for clinical laboratory evaluation results. Virology and (or) pregnancy exam will be listed separately.

### 5.6.3 Vital Sign

Vital signs will be summarized by visit for absolute values and changes from baseline using descriptive statistics.

Shift table of normal/abnormal status from baseline to post-baseline will also be provided.

Listing will be provided for vital sign results.

### 5.6.4 ECG

Worst post baseline QTc will be summarized according to  $\leq 450$ ms,  $>450-480$ ms,  $>480-500$ ms,  $>500$ ms categories and increase from baseline by  $\leq 30$ ms,  $>30-60$ ms,  $>60$ ms. On-treatment period is defined as the period from first dose of study treatment until the last dose of study treatment +90 days including both scheduled and unscheduled visits and repeated visits.

Listing will also be provided ECG results.

**5.6.5 Other safety measurements**

Listing will be provided for physical exam and ECOG.

**5.7 IMMUNOGENECITY ANALYSIS**

Immunogenicity is evaluated by ADA and NAb positive rates. Analyses of immunogenicity in SS include:

Baseline ADA/Nab positive rate and number of positive subjects

Post-baseline ADA/Nab positive rate and number of positive subjects at each timepoint

Further summary of post-baseline data by baseline status

Number and percentage of subjects with persistent/transient post-baseline positive ADA/NAb Listing will also be provided for ADA titre values. Only subjects with at least one non-missing post-baseline ADA result will be included in post-baseline positive rate calculation.

**5.8 PD/BIOMARKER ANALYSIS**

A separate analysis plan will be provided.

**5.9 QUALITY OF LIFE**

The EORTC QLQ-C30 is a core questionnaire for patients with cancer consisting of 30 items which are divided into 15 scales: 5 functional scales (physical, role, cognitive, emotional, and social function), 3 symptom scales (fatigue, pain, and nausea/vomiting), 1 global health status/quality of life scale, and 6 single item scales. The value of EORTC QLQ-C30 score is between 0 and 100.

Definition of EORTC QLQ-C30 dimensions:

	Numbers of Items	Item Range	Item numbers
Overall health and Quality of Life	2	6	29, 30
Function dimension			
Physical function	5	3	1~5
Role function	2	3	6, 7
Emotional function	4	3	21~24
Cognitive function	2	3	20, 25
Social function	2	3	26, 27
Symptom dimension			

## STATISTICAL ANALYSIS PLAN

Innovent Biologics (Suzhou) Ltd  
Protocol number: CIBI308D201

Version: 2.0  
Version Date: 2020-02-28

Weak	3	3	10, 12, 18
Nauseated and vomited	2	3	14, 15
Pain	2	3	9, 19
Short of breath	1	3	8
Poor sleep	1	3	11
Lacked appetite	1	3	13
Constipated	1	3	16
Diarrhea	1	3	17
Financial difficulties	1	3	28

Raw Score (RS) is the mean of each term,  $RS = (I1+I2+ \dots +In) /n$ . Missing items are excluded from the calculation of the mean.

$$\text{Function dimension: Score} = \left(1 - \frac{RS - 1}{\text{range}}\right) \times 100.$$

For change from baseline, descriptive summary will be used.

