8.4.5 Quality of life analysis

The EQ-5D-5L and EROTC QLQ-C30 scores at each evaluation time point will be calculated. The overall score and each dimension score at each time point, as well as relative changes from baseline, will be summarized using descriptive statistics.

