Appendix 9: EORTC-QLQ-C30 (v3) Quality of Life Scale

We would like to know about you and your health status. Please answer all the questions yourself by circling the number that best applies to you. There are no "right" or "wrong" answers. The information that you provide will be kept confidential.

Please fill in your initials: _____

Date of Birth: _____ YYYY_____MM_____DD

Today's date: _____ YYYY_____MM_____DD

	Not at All	A Little	Quite a Bit	Very Muc h
1. Do you have any trouble doing strenuous activities, like carrying a heavy shopping bag or a suitcase?	1	2	3	4
2. Do you have any trouble taking a long walk?	1	2	3	4
3. Do you have any trouble taking a short walk outside of the house?	1	2	3	4
4. Do you need to stay in bed or a chair during the day?	1	2	3	4
5. Do you need help with eating, dressing, washing yourself or using the	1	2	3	4

During the past week:

	Not at All	A Little	Quite a Bit	Very Muc h
6. Were you limited in doing either your work or other daily activities?	1	2	3	4
7. Were you limited in pursuing your hobbies or other leisure time activities?	1	2	3	4
8. Were you short of breath?	1	2	3	4
9. Have you had pain?	1	2	3	4
10. Did you need to rest?	1	2	3	4
11. Have you had trouble sleeping?	1	2	3	4
12. Have you felt weak?	1	2	3	4
13. Have you lacked appetite?	1	2	3	4

14. Have you felt nauseated?	1	2	3	4
15. Have you vomited?	1	2	3	4
16. Have you been constipated?	1	2	3	4

During the past week:

	Not at All	A Little	Quite a Bit	Very Muc h
17. Have you had diarrhea?	1	2	3	4
18. Were you tired?	1	2	3	4
19. Did pain interfere with your daily activities?	1	2	3	4
20. Have you had difficulty in concentrating on things, like reading a	1	2	3	4
21. Did you feel tense?	1	2	3	4
22. Did you worry?	1	2	3	4
23. Did you feel irritable?	1	2	3	4
24. Did you feel depressed?	1	2	3	4
25. Have you had difficulty remembering things?	1	2	3	4
26. Has your physical condition or medical treatment interfered with your	1	2	3	4
27. Has your physical condition or medical treatment interfered with your	1	2	3	4
28. Has your physical condition or medical treatment caused you financial	1	2	3	4

For the following questions, please circle the number between 1 and 7 that best applies to you

29. How would you rate your overall health during the past week?

1 2 3 4 5 6 7

Very poor

Excellent

30. How would you rate your overall quality of life during the past week?

1	2	3	4	5	6	7
Very poor						Excellent

Summary of Amendment

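### SAP 5.9 sets no minimum number of answered items for a QLQ-C30 scale, so physical, emotional and fatigue scores can rest on a small minority of unlike items

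*SAP*

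**What the plan says.** SAP 5.9 divides the 30 items into 15 scales and gives each scale's number of items, item range and item numbers. The physical row reads "Physical function 5 3 1~5": five items, range 3, items 1 to 5. On scoring, the SAP says "Raw Score (RS) is the mean of each term", written as RS = (I1 + ... + In)/n, and then "Missing items are excluded from the calculation of the mean". For function scales the score is (1 − (RS − 1)/range) × 100. The section also says "The value of EORTC QLQ-C30 score is between 0 and 100" and "For change from baseline, descriptive summary will be used".

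Protocol 8.4.5 says "The EQ-5D-5L and EROTC QLQ-C30 scores at each evaluation time point will be calculated" and plans descriptive summaries of the scores at each time point as well as of the changes from baseline.

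No other section supplies a minimum. SAP 4.3 deals with dates, efficacy, baseline, safety and laboratory values. SAP 5.1 deals with percentage denominators. Protocol 6.6 describes the instruments and when they are completed. The SAP reference list names no scoring manual, so a minimum cannot be read in by reference.

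**The concern.** Items within a scale are not interchangeable. In Protocol Appendix 9, item 1 of the physical scale asks "Do you have any trouble doing strenuous activities, like carrying a heavy shopping bag or a suitcase", while item 5 begins "Do you need help with eating, dressing, washing yourself or using the". A patient limited by illness may well answer badly on the first and well on the last. A mean over one or two of these items measures something different from a mean over all five.

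If a patient answers all items at baseline and only some later, the change from baseline can reflect which items were left blank rather than any change in the patient. A programmer following SAP 5.9 to the letter would score every such form, and the output would not show which scores rested on one or two answers. Quality of life is a stated secondary objective and the trial is small, so a few such scores could be visible in a mean.

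**Working it through.** **Inputs.** From SAP 5.9: RS is the mean of the answered items, range = 3, function score = (1 − (RS − 1)/3) × 100, and scores lie between 0 and 100. The answer patterns below are assumptions; the documents contain no item-level data.

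**Step 1: reproduce the stated bounds.** All items 1: RS = 1, score 100. All items 4: RS = 4, score 0. Both match the SAP.

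**Step 2: confirm what n is.** Suppose n stayed at 5 with one item answered 1. Then RS = 1/5 = 0.2 and the score is (1 + 0.8/3) × 100 = 126.7, outside the bounds. So n must be the number of answered items, as the exclusion sentence implies.

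**Step 3: physical scale, assumed answers 4, 3, 2, 1, 1.** With all items answered, RS = 11/5 = 2.2 and the score is (1 − 1.2/3) × 100 = 60. The lowest score at each count keeps the worst answers and the highest keeps the best. For example, two items 4 and 3 give RS = 3.5 and a score of 16.7; three items 2, 1, 1 give RS = 1.333 and a score of 88.9. The last column is the score minus 60, the apparent change for a patient whose state is unchanged and whose baseline form is complete.

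| Items answered | Lowest score | Highest score | Apparent change |
|---|---|---|---|
| 1 | 0.0 | 100.0 | −60.0 to +40.0 |
| 2 | 16.7 | 100.0 | −43.3 to +40.0 |
| 3 | 33.3 | 88.9 | −26.7 to +28.9 |
| 4 | 50.0 | 75.0 | −10.0 to +15.0 |
| 5 | 60.0 | 60.0 | 0 |

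**Step 4: a milder pattern, 3, 2, 2, 1, 1.** Full score: RS = 9/5 = 1.8, score 73.3. One item gives 33.3 to 100, two give 50.0 to 100, and three give 55.6 to 88.9.

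**Step 5: emotional scale (four items), assumed 3, 2, 1, 1.** Full score: RS = 7/4 = 1.75, score 75. One item gives 33.3 to 100, and two give 50 to 100.

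**Step 6: which scales a minimum of half would change.** The SAP table has six single-item scales, six two-item scales (global, role, cognitive, social, nausea/vomiting, pain), and three longer ones: fatigue with 3 items, emotional with 4 and physical with 5. Check: 6 × 1 + 6 × 2 + 3 + 4 + 5 = 30 items. Single-item scales cannot be partly missing. For two-item scales one answer is already half, so nothing changes. The rule bites only when at most 2 of 5 physical, 1 of 4 emotional or 1 of 3 fatigue items are answered.

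**Step 7: effect on a mean.** The amendment summary reports 28 patients enrolled. One spurious change of −60 would move a mean over 28 by 60/28 = 2.1 points. If only 10 patients contributed at a visit (an assumption), it would move the mean by 60/10 = 6 points.

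**The case against.** The strongest reply is that this is an edge case. The SAP states a definite, reproducible rule, and scoring from one of five items is an inference from the absence of a minimum. The 0 to 100 range needs four of five items blank and answers spanning the whole response scale. Appendix 9 asks patients to answer every question, and nothing in the documents shows that sicker patients skip items. No test, threshold or comparison uses these scores. All of this stands as a limit on size. It does not supply a minimum, and the rule as written does produce such scores.

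A second reply is that the remedy is partial. With three of five items answered, the Step 3 example still ranges from 33.3 to 88.9. A two-item scale answered 3 and 1 has a full score of 66.7 but gives 33.3 or 100 from one item, with or without the minimum. That is correct. The documents also do not single out one half as the threshold; it is a prespecified choice that cuts off the widest ranges.

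Three stronger readings are tempting and not supported:

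- A reader might infer that the whole questionnaire is unreliable. Six of the 15 scales are single items, and for six more the proposed minimum changes nothing.
- A reader might infer that the reported scores will be badly wrong. The documents give no rate of partly completed forms, so the actual effect is unknown.
- A reader of the SAP alone might infer that change from baseline is the only QLQ-C30 analysis. Protocol 8.4.5 also summarises the scores at each time point; those use the same rule.

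**Conclusion.** The point holds in a limited form. SAP 5.9 lets the physical, emotional and fatigue scales be scored from a small minority of their items, and nothing elsewhere prevents it. Under the assumed physical answers, the possible score is 0 to 100 from one item and 16.7 to 100 from two, against 33.3 to 88.9 from three and a full score of 60. These are worst cases from a constructed pattern; the milder pattern gives narrower ranges. The effect is zero if forms are complete or if a patient's answers within a scale are all equal. Only a descriptive secondary endpoint is affected; the ORR analysis and its conclusion are not. This is a worthwhile clarification of low severity.

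**What to change.** Add to SAP 5.9 that a multi-item QLQ-C30 scale score is computed only when at least half of the scale's items are answered: 3 of 5 for physical, 2 of 4 for emotional and 2 of 3 for fatigue. Two-item scales still need one answer, so they are unchanged. Below the minimum, set the score to missing. Report, by visit and scale, the number of scores set to missing for this reason.

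The cost is one sentence, one extra count in the tables and probably a few missing scores. In the physical example the possible apparent change narrows from −60.0 to +40.0 down to −26.7 to +28.9, so the dependence on blank items is reduced but not removed. The counts would show how often scores fell below the minimum.
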